This study also includes a Data Safety Monitoring Plan as submitted to and approved by the study sponsor: National Institutes of Health and National Heart, Lung, and Blood Institute. A formal Data Safety and Monitoring Board has been assembled for this project. The plan for safety and monitoring is as follows.

14. Data and Safety Monitoring

Data Quality Monitoring

Principal investigator, [name], will take responsibility that the study is adequately monitored and that the data are secure. Co-investigators, [name] and [name] each have human subject protection certifications through their institutions. All UofR recruitment staff will have human subject protection certifications prior to recruiting subjects into the study and will be included in the IRB application. Recruitment will only occur at the University of Rochester. There will be no enrollment of subjects at the University of Boston Medical Center or Johns Hopkins University.

Research assistants/interviewers will be responsible for all assessments, and will receive training from key study personnel regarding asthma terminology, symptoms, and medication understanding. They will be trained by the study coordinator on the use of the spirometer, FeNO machine, scale, stadiometer, and salivary collection methods.

Data forms will be completed at each study home visit or telephone interview and will be returned with a cover sheet and other source documentation support materials (informed consent, contact information, etc.). Pre-intervention training of study staff will be conducted to increase knowledge about asthma, asthma medications, and other important information in order to reduce the number of “real-time” data collection errors. Through this training, staff will note any inconsistencies in parent reported data and will discuss them with the parent at the time of the interview.

Once forms have been collected, errors that can be corrected over the telephone (legibility, incorrect dates, etc.) will be done using telephone interviews with the parents. Forms will be keypunched into the database using a double-entry system technique and checklists will be used to ensure that all data forms have been received and entered into the database. Simple range checks as well as cross-form validation checks will be performed to ensure the accuracy and completeness of the data. A list of all data checks performed will be maintained and any errors detected by this method will be noted on the form (initials and date of change). In addition, data forms, valid informed consent documents for each enrolled patient, and supporting source documentation materials will be reviewed by the information analysts for accuracy. Required regulatory documents (IRB approval, updates to the protocol, data monitoring documents) will be maintained by the study coordinator. All events during the course of the trial including study enrollments, adverse events and study terminations will be reported to the study coordinator (see Safety Monitoring section below).

Safety Monitoring

A Data Safety Monitoring Board (DSMB) including a pediatric allergy and immunology specialist ([name]; Arkansas Children’s Hospital Research Institute), an epidemiologist ([name], MS, PhD; Temple University), and a human subjects specialist ([name], MS, MPA; Department of Pediatrics, University of Rochester), has been assembled to provide ongoing oversight of the study. The DSMB will meet bi-annually or more frequently as needed to review study procedures and data. Potential risks related to participation in this study are minimal since the medications delivered through this program are routinely recommended by national guidelines for asthma care. In our previous school-based asthma program, which included 530 children, there were no reports of significant adverse events. The frequency and severity of all reported adverse events will be systematically recorded at each follow-up interview. Telephone interviewers will inquire about any adverse events, and specifically ask about any yeast infections of the mouth and facial rash. Any significant adverse events will be flagged by the follow-up research associates and relayed promptly to the senior study coordinator, the principal investigator, the child’s health care provider, the Institutional Review Board, the DSMB, and the NIH within 24 hours. We will hold bi-weekly research review meetings with the study team to

provide an additional layer of monitoring to ensure subject safety as well as treatment integrity.

All records will be kept strictly confidential as required by the policies and procedures of the University of Rochester where data are collected, processed, and reported.

15. Potential Benefits

Adolescents may or may not benefit from the study. They may experience improved asthma morbidity due to the additional time and attention they receive around their asthma and asthma care. Additionally, teens in the groups receiving preventive medications may experience reduced symptoms due to taking their medication daily. In addition, the teen's health care provider will be alerted of their asthma severity, and families will receive telephone calls in order to assess the teen's ongoing symptoms. It is possible that an increased awareness of symptoms and enhanced communication with the health care provider will occur, and will result in improved asthma care and reduced morbidity for these adolescents.

16. Analysis

Sample Size and Power Justification:

This study is designed to have adequate power to test the primary hypothesis that teens receiving SB-ACT will have more symptom-free days at the 3, 5, and 7 -month evaluations compared to AE. Previous asthma interventions, including the SBAT trial, have demonstrated that improvements of 0.9 SFD/2 weeks are feasible and clinically meaningful.^{47,48} Based on our prior data, we estimate a pooled standard deviation (SD) of SFD to be 2.6 and within-subject correlation (ICC) of 0.3-0.4. We calculated power for the intervention effect on SFD while justifying repeated assessments for outcomes (5, 7, 12 months). A sample size of 123 subjects per group will obtain 94-96% power to detect a difference of 0.9 in SFD at a two-sided 5% significance level (assuming ICC: 0.3-0.4). We anticipate <15% attrition, as attrition was minimal (<5%) in the prior study, and therefore plan to enroll 430 teens. To test the short term intervention effect of DOT-only vs. AE, the sample size of 123 per group will obtain 80% power to detect a difference of 0.93/2 weeks at 3-month assessment with a two-sided 5% significance. We expect the DOT-only intervention won't sustain the effect at long term follow-up compared with AE. To test this, the proposed sample size will have 86% power at a one-sided 5% significance level, using a non-inferiority test with a margin of equivalence of 0.9 and a SD of 2.6. To compare the long-term effect of DOT-only vs. SB-ACT, we will have 80% power to detect an effect size of 0.4 at a two-sided 5% significance level.

To evaluate the intervention effect *within* each study arm, we anticipate in the SB-ACT group the rate of asthma control, asthma exacerbation and no absences will reach a guideline-based target of 80%. 123 subjects will have 80% power to claim a rate $\geq 80\%$ with a non-inferiority margin to be 10%, at a one-sided significance level of 5%.

There are 10,900 teens in 7th-10th grade in the city school district and >6,000 entering 7th graders in a 3 yr. period. Conservatively assuming an asthma prevalence of 10%,¹ >1,690 of these students have asthma, and approximately 1/2 have persistent asthma. In our prior study, we enrolled 74% of eligible subjects. We can conservatively enroll 126 subjects/year (60%); which is more than adequate for sample size requirements.

Primary Analysis:

We will use graphs and descriptive statistics to summarize outcomes by intervention group at each time point. We will assess for differences between groups at baseline despite randomization (e.g., demographics, depressed mood, school/neighborhood factors) to enable the identification of covariates to be controlled in later analyses. If distributional

assumptions associated with a particular statistical procedure are violated, we will use appropriate transformations or non-parametric alternatives. Analysis will be performed under the intent-to-treat principle.⁴⁹ Hypothesis-driven comparisons will be made to control the family-wise type I error rate at 0.05 (2-sided) for primary hypotheses.

We expect minimal loss to follow-up.^{13,47,50} Inferences are valid if missing data follows the missing completely at random (MCAR) assumption.⁵¹ However, the occurrence of missing data may depend on the observed response, thus we will perform sensitivity analysis to examine the MCAR assumption. If it is severely violated, we will report treatment effects using weighted GEE to address MCAR. Biased estimates may also arise in the case of non-ignorable non-response (NINR). Although unanticipated, we will examine NINR using the joint modeling approach.⁵² For SEM, the maximum likelihood estimates (MLE) are valid under MAR, if the posited distribution models are satisfied. In the presence of missing data, estimates from LMM and SEM may be biased if parametric assumptions are not met, even with the use of robust variance estimates. If this arises, we will change the distribution models and/or use clustered bootstrap methods for inference.⁵³

REFERENCES:

3. *Expert Panel Report II: Guidelines for the Diagnosis and Management of Asthma-Update on Selected Topics 2002*. NIH publication no. 02-5075. Bethesda, MD: US Department of Health and Human Services; National Heart, Lung, and Blood Institutes; National Asthma Education and Prevention Program;2002.

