Adolescents 12-16 years of age attending secondary school in the Rochester City School District (RCSD) and surrounding school districts will be screened for eligibility at the start of the school year. A total of 430 teens will be recruited over 4 years from approximately 20 schools. School-based screening, used successfully in our past programs, will identify teens for the program. In compliance with the Family Education Rights and Privacy Act, our study has access to the RCSD medical alert forms that include whether or not the teen has a breathing problem. For the surrounding school districts, school nurses or administrators will contact caregivers of potentially eligible families, and if the family is interested, will connect the caregiver with the study team for an eligibility assessment. Additionally, we will review potentially eligible teens from [name] Contact Database (RSRB# 31010) to inquire if prior study participants are eligible and interested in the current study. We will assess

eligibility for the study by a telephone survey with the primary caregiver.

Eligibility requirements include:

- 1) Physician-diagnosed asthma (based on caregiver report).
- 2) Persistent asthma severity or poor asthma control (based on national guidelines⁴ and caregiver report). Per NHLBI EPR-3 criteria, any 1 of the following:
 - a. In past month, >2 days/week with daytime asthma symptoms
 - b. In past month, >2 days/week with rescue medication use
 - c. In past month, >2 times/month with nighttime awakening due to asthma symptoms
 - d. ≥ 2 asthma exacerbations during past year that required oral systemic corticosteroids
- 3) Age ≥ 12 and ≤ 16 years
- 4) Attending secondary school in the Rochester City School District or surrounding school districts.

Exclusion Criteria:

- 1) Inability to speak and understand English.
- 2) No access to a working phone for follow-up surveys (either at home or an accessible alternate location).
- 3) Diagnosed developmental or intellectual disability.
- 4) Other significant medical conditions, including congenital heart disease, cystic fibrosis, or other chronic lung disease, that could interfere with the assessment of asthma-related outcome measures.
- 5) Teens in foster care or other situations in which consent cannot be obtained from a legal guardian.

Based on our previous studies, we anticipate <10% of subjects to be excluded based on these criteria.

C. Study Procedures

1. Screening procedures

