Screening will occur from late summer (as soon as school enrollment forms are available to the team) until the end of January (since new screening information becomes available during the first few months of school). To evaluate subjects for eligibility, screening procedures occur up to 4 weeks prior to the baseline assessment and randomization. The baseline assessment includes symptom questions to be assessed for all teens and will be reviewed for teens that we are unable to complete the baseline within 4 weeks of the screening survey.

We will identify teens through school “medical-alert” forms that include whether or not the child has a breathing problem or referral from school nurse. All teens who have a breathing problem indicated on their medical-alert forms will be identified. We will conduct a telephone screening survey with the caregiver to assess eligibility, and only teens with persistent symptoms or poor asthma control will be eligible. Enrollment and randomization occur in a rolling fashion from the first day of school until the end of February (since enrollment can occur up to 4 weeks after screening survey completion).

2. Baseline

Home visits will be used to explain the study, elicit informed consent from the parent and assent from the teen, and obtain baseline measurements. Baseline evaluations include: confirmation of inclusion/exclusion criteria, assessment of baseline severity, collection of demographic and health history variables, measurement of pulmonary function (using a

portable spirometer), exhaled nitric oxide (FeNO – for airway inflammation), salivary cotinine, height, and weight. All surveys questions will be read aloud to caregivers and teens. We will give a symptom diary to the teen and caregiver for symptom tracking, assist in finding a prominent location for it, and review its use. For home interviews in which the child is not present, we will determine another time to come to the home to obtain the teen's assent, conduct the baseline surveys, and collect samples and measurements. If it becomes difficult to reach the child at home we will ask the parent's permission to meet with the child at the school nurse's office to obtain assent, and collect the cotinine, FeNO, spirometry, and height and weight measurements. We will then contact the child by phone to complete the baseline survey. (*Note: If teen refuses to assent to the study, the study subject will be withdrawn and all study materials will be destroyed.*)

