Motivation	Teen - Medication Adherence Motivation and Confidence	Baseline, each follow-up
Beliefs about Medications	Teen and caregiver – Beliefs about Medications Questionnaire (BMQ)	Baseline, 7-month
	Teen – Beliefs About Medications – Intent to Adhere Subscale (BAMS-IA), Asthma Readiness to Change Questionnaire	Baseline, 7-month
Process Evaluation		
RE-AIM Summary Measures See detailed table in Process Evaluation section below	RE-AIM Dimensions and Questions for Evaluating Health Education and Health Behavior Research	At end of each study year

* Parents and teens whose scores indicate they may be suffering from mild to severe depression will be provided a list of mental health services and providers in the community, and will be referred to their primary care provider.

10. Compensation

Teens and caregivers will each receive a \$20 gift card following baseline survey, \$10 after the 3- and 5- month follow-ups, and \$30 after the 7- and 12- month follow-ups. Payment to participants will be in the form of a prepaid Visa debit card from Bank of America. The use of these cards allows for tracking the use of lost or stolen cards and provides flexible options for participant use.

11. Process Evaluation

We will consider both individual and institutional level impacts and resources available in 'real world' schools and communities. We will use **RE-AIM**⁴⁴ metrics to assess :1) the

proportion of eligible subjects who participate and the representativeness of participants compared to non-participants (*Reach*), 2) the intervention’s impact on primary outcomes and quality of life (*Effectiveness*), 3) characteristics of schools and program support by school administration, nurses, providers, and teens/caregivers (*Adoption*), 4) the consistency in delivery of each intervention component (including the efficiency of the delivery of medication to the schools, the % of days teens receive medications in school, % completed counseling sessions, and whether additional contacts with the nurses occur beyond the intervention period) (*Implementation*), and 5) the extent to which intervention components continued or were modified post-study completion and its long-term effects (*Maintenance*). The final interview will also include Likert-scale and open-ended questions to teens, parents, PCPs, school nurses and administrators about convenience, scheduling, and satisfaction.

RE-AIM METRICS		
RE-AIM	QUESTIONS	ASSESSMENT METHOD

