Reach (Individual Level)	What percent of eligible participants: a) were excluded, b) took part and c) how representative were they?	Response rate and demographics
Effectiveness (Individual Level)	Effect of intervention on primary outcomes and QOL? Were pre-determined NHLBI guideline-based targets achieved?	Primary analysis (symptoms, quality of life; economic evaluation)
Adoption (Setting/Staff Level)	Characteristics of participating secondary schools, time and resource burden on school and community personnel.	School characteristics, demographics, staff surveys
Implementation (Setting Level)	To what extent were the various intervention components delivered as intended by school and community staff members?	Medication delivery log, session completion rate, contacts with nurses, surveys
Maintenance (Individual Level)	Long term effects at 12 months? Attrition rate? Were drop-outs representative; how did attrition impact conclusions?	Analysis of long-term outcomes (12 month assessment), attrition, demographics
Maintenance (Setting Level)	a)To what extent were intervention components continued post-study completion, b)how was the program modified	Survey and semi-structured interviews with school nurses, administrators, ALA leadership

12. Data Storage and Confidentiality

To maintain the integrity, security, and confidentiality of study data, the data will be maintained in a secure and encrypted web-based database and/or a password protected database on a secure university network drive. No subject data will be stored on the internal hard drives of any Strong Health computers. After data validation and analysis, subject information will be de-identified. All consent forms, paper surveys and additional correspondence will be locked in an office or filing cabinet and will only be accessible by the study staff.

Baseline, follow-up, and chart review data will be entered into a password-protected database. This database is stored on a secure university network drive that is only accessible by the research team whom must use their NetID and password to access the database. Data may also be collected and stored using RedCap, a secure, password protected database (using University NetID’s and passwords) hosted through the University of Rochester.

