The counseling and education sessions will be audio recorded. These recordings will be saved on Box.net, a secure and University supported database that will only be accessible by investigators and study personnel. These recordings will be used for supervision of the counseling and education sessions to ensure the protocol is being followed correctly.

Portions of the final assessments with caregivers, nurses, and healthcare providers may be tape recorded too. These recordings will be saved on a university network drive that is only accessible by study personnel whom must use their NetID and password to access these tape recordings. Once the recordings have been transcribed, they will be deleted from the network drive.

The Rochester City School District has partnered with the University of Rochester study team for this study, and all of the procedures follow the school district's rules of privacy and confidentiality, as outlined in the letter from [name], Chief of Accountability for the Rochester City School District. As deputies of the school district, the study team is granted permission to review limited student information and contact families to inquire about their willingness to participate in the study.

For surrounding school districts, the study team will not have access to student data until the family has consented to the study procedures.

13. Safety

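### In the surrounding districts only families already interested reach the eligibility survey, so a Reach figure combined across recruitment routes would be overstated and should be reported by route

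*Combined protocol and SAP*

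**What the plan says.** Study Objective 8 is to evaluate implementation with RE-AIM metrics. Section 11 (Process Evaluation) describes Reach as the "proportion of eligible subjects who participate and the representativeness of participants compared to non-participants". The RE-AIM table in the same section asks "What percent of eligible participants: a) were excluded, b) took part and c) how representative were they", to be assessed from the response rate and demographics. No breakdown by recruitment route is described.

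Section B (Subjects and Setting) says the team will assess "eligibility for the study by a telephone survey with the primary caregiver". Teens arrive at that survey by three routes:

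- **City district.** The team has the medical-alert forms. Section C.1 (Screening procedures) states: "All teens who have a breathing problem indicated on their medical-alert forms will be identified". Their caregivers are then telephoned.
- **Surrounding districts.** School nurses or administrators contact caregivers first and, "if the family is interested, will connect the caregiver with the study team for an eligibility assessment". Section 12 (Data Storage and Confidentiality) adds: "For surrounding school districts, the study team will not have access to student data until the family has consented to the study procedures".
- **Contact database.** The team itself asks former study participants whether they are eligible and interested.

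Section C.2 (Baseline) says that if a teen refuses assent, "the study subject will be withdrawn and all study materials will be destroyed".

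**The concern.** A participation proportion needs a denominator that is observed in the same way for everyone it covers. Here a family becomes known as eligible only by completing the telephone survey. In the surrounding districts a filter on willingness stands in front of that survey. Eligible families who say no to the school nurse are not surveyed, not counted and not described, whereas a city family who completes the survey and then declines is counted as an eligible non-participant.

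Reach supports the stated aim of evaluating widespread implementation. A combined figure would credit the programme with better uptake than it had, by an amount that grows with the surrounding-district share. The comparison of participants with non-participants would also lack the earliest refusers, and its recorded non-participants would come mostly from the city district.

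**Working it through.** **The plan's own figure.** The only current-trial number on the Reach scale is the 60% enrolment assumption in Section 16 (Sample Size and Power Justification). It reproduces: (10,900 + 6,000) × 10% = 1,690 teens with asthma; × 1/2 = 845 with persistent asthma; × 0.60 = 507; ÷ 4 years = 126.75 a year, against the stated 126. This figure is not in dispute. Its source population is the city district only.

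**Inputs**

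- r, city-district Reach: 60% (planning figure), with 74% (prior study) as an alternative. Both are in Section 16.
- s, surrounding-district share of eligible teens: not in the documents; assumed 5% to 30%.
- q, share of those eligible families who say they are interested and are passed on: not in the documents; assumed 30% to 70%.
- c, participation once surveyed on that route: not in the documents; assumed 90%.

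**Formulas.** The contact-database route is set aside and the city denominator is taken as recorded, to isolate the effect of the interest filter.

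- Full Reach = (1-s)r + s·q·c
- Recorded Reach = [(1-s)r + s·q·c] / [(1-s) + s·q]
- Recorded ÷ full = 1/[(1-s) + s·q] = 1/[1 - s(1-q)]

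The ratio does not depend on r or c. It exceeds 1 whenever s > 0 and q < 1, and equals 1 if every eligible family is interested.

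**Results with r = 60%, c = 90%, q = 50%**

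| s | Full Reach | Recorded Reach | Excess (points) | Ratio |
|---|---|---|---|---|
| 10% | 0.540 + 0.045 = 58.5% | 0.585/0.95 = 61.6% | 3.1 | 1.05 |
| 20% | 0.480 + 0.090 = 57.0% | 0.570/0.90 = 63.3% | 6.3 | 1.11 |
| 30% | 0.420 + 0.135 = 55.5% | 0.555/0.85 = 65.3% | 9.8 | 1.18 |

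Over s = 5% to 30% and q = 30% to 70%, still with c = 90%, the excess is about 1 to 13 points at r = 60% and about 1 to 16 points at r = 74%.

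A second illustration sets true participation at 60% on both routes. With c = 90% this implies q = 0.60/0.90 = 67%. Recorded Reach is then 62.1% at s = 10% and 64.3% at s = 20%, against a true 60%.

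**Representativeness.** Take s = 30%, r = 60%, q = 50%, c = 90%. As shares of all eligible teens, city participants are 0.42, city non-participants 0.28, surrounding participants 0.135, surrounding decliners after survey 0.015, and uninterested families never recorded 0.15. Two invented trait patterns show the direction is open:

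- *Uninterested families differ more.* Trait in 65% of participants, 70% of recorded non-participants and 85% of uninterested families. All non-participants: (0.28×0.70 + 0.015×0.70 + 0.15×0.85)/0.445 = 75.1%. The true gap is -10.1 points; the recorded gap is 65 - 70 = -5.0. The record looks too favourable.
- *Districts differ.* Trait in 80% of all city teens and 40% of all surrounding-district teens. Participants: (0.42×0.80 + 0.135×0.40)/0.555 = 70.3%. All non-participants: 0.290/0.445 = 65.2%, a true gap of +5.1. Recorded non-participants: 0.230/0.295 = 78.0%, a recorded gap of -7.7. The record is less favourable and has the opposite sign.

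**The case against.** The plan never says the routes will be pooled; that is inferred from one definition and no breakdown. Section 12 restricts student data before consent, not aggregate counts from schools. The size depends on shares the documents do not give, and the city-only feasibility count (126 × 4 = 504) already exceeds the 430 target, so nothing points to a large surrounding-district share. Reach is descriptive. All of this stands. It limits the size of the point but does not remove the missing denominator.

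Several stronger readings are tempting, and the documents do not support them:

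- *The representativeness comparison will look too good.* Its direction depends on how uninterested families and the districts differ, which is not stated.
- *City Reach is complete.* City families who are not reached or who refuse the telephone survey are not classed as eligible either. The routes differ in degree.
- *The contact database has the same gap.* It is a selected population, but the team makes those contacts itself and can count refusals.
- *Refused assent erases the teen from the count.* Section C.2 speaks of study materials and does not say whether a screening count survives. Section 14 also has enrolments and terminations reported to the coordinator.
- *Every family that declines at the school's call belongs in the denominator.* They are unscreened and only potentially eligible. Section 16 takes about half of students with asthma to have persistent disease. Adding them all could push Reach too low.

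**Conclusion.** The point holds for the Reach proportion, conditionally. If the routes are combined under the single definition in Section 11, Reach is overstated by the factor 1/[1 - s(1-q)] whenever the surrounding districts contribute eligible teens and some of their families decline at first contact. The direction follows from the algebra. The size is illustrative: a factor of 1.05 to 1.18 for assumed s of 10% to 30% and q of 50%. For representativeness the supportable conclusion is that the comparison is incomplete and may err either way. Randomization, the primary outcome and the sample size are untouched. This is a minor point, worth correcting because it concerns a stated objective and costs little.

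**What to change.** In Section 11, text and RE-AIM table:

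1. Report Reach and the participant versus non-participant comparison separately for the city medical-alert, surrounding-district referral and contact-database routes.
2. Label the surrounding-district figure as conditional on prior interest, and note that the city figure is conditional on completing the telephone survey.
3. Where school staff can supply it, collect a de-identified count of caregivers contacted, not reached and declining. Report it as a separate contact-to-referral rate, or as a sensitivity bound: participants ÷ (confirmed eligible + f × decliners), with f an assumed eligible fraction shown over a range. Do not add decliners in full to the confirmed-eligible denominator.
4. Keep a de-identified count of teens who refuse assent, and include it among eligible non-participants.

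The cost is some wording and a tally sheet, which should be kept as contacts happen. No recruitment or privacy rule changes. The downside is that Reach becomes less favourable and is no longer one headline number.
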